#### Secondary objectives

- To compare the efficacy of liraglutide versus placebo on glycaemic control in children and adolescents with obesity and PWS at 16 weeks and versus no treatment at 52 weeks.
- To estimate the liraglutide steady state exposure in children and adolescents with obesity and PWS after 16 weeks of treatment.
- To compare the safety of liraglutide versus placebo in children and adolescents with obesity and PWS at 16 weeks and versus no treatment at 52 weeks.

### 4.2 Endpoints

#### 4.2.1 Primary endpoints

There are two co-primary endpoints:

- Change in body mass index (BMI) standard deviation score (SDS) from baseline to 16 weeks
- Change in body mass index (BMI) standard deviation score (SDS) from baseline to 52 weeks

#### 4.2.2 Secondary endpoints

##### 4.2.2.1 Supportive secondary efficacy endpoints

- Percent of subjects achieving  $\geq 5\%$  reduction in baseline BMI at weeks 16 and 52\*
- Percent of subjects achieving  $\geq 10\%$  reduction in baseline BMI at weeks 16 and 52\*
- Percent of subjects with no increase in BMI SDS at weeks 16 and 52

Change from baseline to 16 and 52 weeks in:

- BMI\*
- Body weight (kilogram (kg), pounds (lb) and percent (%))\*
- Waist circumference
- Waist to hip circumference ratio
- Hyperphagia score:
  - total score and\*
  - hyperphagic behaviour, drive and severity score\*
- Cardiovascular risk factors:

Protocol: Liraglutide  
Trial ID: NN8022-4179  
UTN: U1111-1162-7884  
EudraCT no.: 2014-004415-37

CONFIDENTIAL

Date: 16 July 2020  
Version: 5.0  
Status: Final  
Page: 26 of 125

Novo Nordisk

- High sensitivity C reactive protein (hsCRP)
- Fasting lipids: total cholesterol (TC), low density lipoprotein cholesterol (LDL-cholesterol), high density lipoprotein cholesterol (HDL-cholesterol), non-HDL cholesterol, very low density lipoprotein cholesterol (VLDL-cholesterol), triglycerides (TG), and free fatty acids (FFA)
- Systolic and diastolic blood pressure\*
- Glucose metabolism: glycosylated haemoglobin (HbA1c)\*, fasting plasma glucose (FPG)\*, fasting insulin, fasting C-peptide, glycaemic category, homeostasis model assessment of beta-cell function and insulin resistance parameters (HOMA-B and HOMA-IR)

#### 4.2.2.2 Supportive secondary PK endpoint

Model-derived area under the curve (AUC) over the dosing interval in steady state.

#### 4.2.2.3 Supportive secondary safety endpoints

- Number of treatment-emergent adverse events during the trial
- Number of severe treatment emergent episodes of hypoglycaemia
- Number of blood glucose confirmed symptomatic episodes of hypoglycaemia
- Occurrence of anti-liraglutide antibodies

Change from baseline to 16 and 52 weeks in:

- Electrocardiogram (ECG)
- Pulse
- Laboratory parameters:
  - Haematology: haemoglobin, haematocrit, thrombocytes, erythrocytes, leukocytes, differential count (eosinophils, neutrophils, basophils, lymphocytes, monocytes)
  - Biochemistry: creatinine, creatine kinase (CPK), urea, albumin, bilirubin (total), alanine aminotransferase (ALT), aspartate aminotransferase (AST), alkaline phosphatase, sodium, potassium, calcium total, calcium albumin corrected, amylase, lipase, and carcinoembryonic antigen (CEA)
  - Hormone levels including: calcitonin, insulin-like growth factor-1 (IGF-1), thyroid stimulating hormone (TSH), free thyroxine (free T4), prolactin, adrenocorticotrophic

Protocol: Liraglutide  
Trial ID: NN8022-4179  
UTN: U1111-1162-7884  
EudraCT no.: 2014-004415-37

~~CONFIDENTIAL~~

Date:	16 July 2020	Novo Nordisk
Version:	5.0	
Status:	Final	
Page:	27 of 125	

hormone (ACTH), cortisol, dehydroepiandrosterone sulfate (DHEAS), luteinising hormone (LH), follicle stimulating hormone (FSH), estradiol (females), testosterone (males)

- Pubertal status
- Physical examination including height
- Part A only: Mental health assessed by Columbia Suicidality Severity Rating Scale (C-SSRS) and Patient Reported Health Questionnaire-9 (PHQ-9)

\*Key supportive secondary endpoint prospectively selected for posting on clinicaltrials.gov and EudraCT)

Protocol: Liraglutide  
 Trial ID: NN8022-4179  
 UTN: U1111-1162-7884  
 EudraCT no.: 2014-004415-37

[figure not shown]
CONFIDENTIAL

Date: 16 July 2020  
 Version: 5.0  
 Status: Final  
 Page: 28 of 125  
 Novo Nordisk

## 5 Trial design

### 5.1 Type of trial

This is a multi-centre, multi-national, randomised, parallel group, placebo-controlled trial with a 16-week double-blind period and a 36-week open-label period. This trial consists of a part A and a part B. Part A of the trial is conducted in adolescents ( $\geq 12$  and  $< 18$  years, Tanner stage 2–5) with obesity and PWS. Part B of the trial is conducted in children ( $\geq 6$  and  $< 12$  years, Tanner stage below 2 (defined as Tanner stage 1 with or without premature adrenarche)) with obesity and PWS. Both part A and part B (for children with body weight  $\geq 45$  kg) will follow the trial diagram (Figure 5–1). Part B for children with body weight  $< 45$  kg will follow the trial diagram (Figure 5–2). Entry into part A and part B of the trial will be sequential. After all subjects in part A have completed the 16-week double-blind period, an independent external Data Monitoring Committee (DMC) will review the PK data and safety data from part A. The DMC will recommend to the Novo Nordisk safety committee whether children in part B should be randomised, and exposed to liraglutide/liraglutide placebo. In addition, the tolerability/safety and PK data from trial NN8022-4181 in children with obesity 7-11 years (both inclusive) will be reviewed to allow adjustments in part B, as needed (conclusion after part A; see above).

**Figure 5–1 Trial diagram** (Part A and part B (for children with body weight  $\geq 45$  kg))

Dose escalation can be prolonged to 8 weeks. **Abbreviations:** EOT = end-of-treatment; EOS = end-of-study; MTD = maximum tolerated dose.

\* Placebo injections will end at week 16 for subjects allocated to the placebo arm.

[figure not shown]
Protocol: Liraglutide  
 Trial ID: NN8022-4179  
 UTN: U1111-1162-7884  
 EudraCT no.: 2014-004415-37

CONFIDENTIAL

Date:  
 Version:  
 Status:  
 Page:

16 July 2020  
 5.0  
 Final  
 29 of 125

Novo Nordisk

**Figure 5–2 Trial diagram** (Part B for children with body weight < 45 kg)

Dose escalation can be prolonged to 8 weeks. **Abbreviations:** EOT = end-of-treatment; EOS = end-of-study; MTD = maximum tolerated dose.

\* Placebo injections will end at week 16 for subjects allocated to the placebo arm.

Subjects will be randomised 2:1 to receive liraglutide or liraglutide placebo. Part A has four strata as subjects are stratified according to Tanner stage 2–3 and 4–5 and by presence/absence of dysglycaemia. Part B includes subjects with Tanner below 2 (defined as Tanner stage 1 with or without premature adrenarche) and has two strata for presence/absence of dysglycaemia, see section [11](#).

Dysglycaemia is defined as pre-diabetes with FPG 5.6 – 6.9 mmol/L (both inclusive) (100-125 mg/dL) (both inclusive) and/or HbA1c 5.7 – 6.4 % (both inclusive). The HbA1c and FPG results from V2 must be used.

At least 30% of subjects will be from areas with lifestyle and nutrition comparable to that in the European Union (EU). All subjects and/or their legally acceptable representative (LAR) will undergo counselling for weight loss and must be prescribed a structured programme for diet and physical activity throughout the trial (from randomisation to the end of the trial). Placebo injections will be stopped at week 16, at the end of the double-blind period.

Subjects treated with growth hormone therapy may enter the trial and will have no change in treatment plan with growth hormone from randomisation to the end of the open-label period (subjects on growth hormone will stay on, and subjects off growth hormone will stay off during this period. Adjustments to doses of growth hormone are permitted).

Protocol: Liraglutide  
Trial ID: NN8022-4179  
UTN: U1111-1162-7884  
EudraCT no.: 2014-004415-37

~~CONFIDENTIAL~~

Date: 16 July 2020  
Version: 5.0  
Status: Final  
Page: 30 of 125

**Novo Nordisk**

## 5.2 Rationale for trial design

This trial is designed in accordance with regulatory requirements (FDA 21 CFR 314.126) and recommendations from the literature.

The design has been chosen in accordance with the trial objectives and with input from the Paediatric Committee (PDCO) of the European Medicines Agency's (EMA).

The co-primary efficacy endpoints are change in BMI SDS from baseline to 16 weeks and 52 weeks. Change in BMI SDS is selected based on the EMA recommendation regarding the assessment of efficacy of new medicinal products for the treatment of obesity in children. The first 16 weeks will be placebo-controlled and double-blinded to evaluate the effect of liraglutide versus placebo, as an adjunct to a structured program for diet and physical activity. The 36-week open-label period will provide supportive evidence to evaluate the continued efficacy and safety of liraglutide. Placebo injections will be stopped at the end of the double-blind period to avoid inconvenience to the subjects.

The rationale for choosing a treatment duration of 16 weeks for the primary efficacy endpoint is that this time period is considered adequate to show effect of liraglutide treatments on the endpoint, and to minimise the duration of placebo injections. The 36-week open-label period will allow additional time to evaluate the full effect of liraglutide on other efficacy endpoints including BMI, body weight, waist to hip circumference, cardiovascular risk factors (hsCRP and lipid profile), blood pressure and glucose metabolism and safety assessments. Furthermore, a 52-week total trial period is regarded to be sufficient to characterise the safety and tolerability profiles of liraglutide.

A 2:1 randomisation was chosen to ensure more subjects will receive active treatment with limited number of subjects enrolled in the trial, and therefore more safety data on liraglutide treatment is obtained.

The PK properties of liraglutide (i.e. exposure) in children and adolescents with PWS will be evaluated by population PK modelling, allowing for sparse PK sampling. The sparse sampling is implemented to reduce the burden on trial subjects and their LAR. The number of samples per subject has been chosen to allow for an adequate precision on the individual estimate for apparent clearance, CL/F. This parameter is used to derive exposure (AUC), thus allowing for a comparison with other relevant populations (such as adults with obesity, children with obesity and adolescents with obesity without PWS). Although sampling during the whole dosing interval will give adequate information on CL/F, the timing of sampling in the dosing interval has been optimized (mostly through samples) to improve precision of the CL/F estimate.

Protocol: Liraglutide  
Trial ID: NN8022-4179  
UTN: U1111-1162-7884  
EudraCT no.: 2014-004415-37

~~CONFIDENTIAL~~

Date: 16 July 2020  
Version: 5.0  
Status: Final  
Page: 31 of 125

**Novo Nordisk**

### 5.3 Treatment of subjects

Liraglutide or liraglutide placebo will be administered by once-daily subcutaneous (s.c.) injections either in the abdomen, thigh, or upper arm; injection site consistency is not required throughout the trial. During the 16-week double-blind period, subjects randomised to receive liraglutide placebo will receive placebo s.c. injections with injection volumes equivalent to the corresponding liraglutide dose. Liraglutide placebo contains the same excipients as liraglutide, but no active trial product. Injections can be administered at any time of day irrespective of meals. It is recommended that the time of injection is consistent throughout the trial. Subjects will be instructed to perform an air shot before the use of a new pre-filled pen. At the end-of the double-blind period, subjects randomised to receive placebo will stop injections once the investigator and subject are un-blinded to treatment allocation. During the 36-week open-label period, subjects in the liraglutide group will continue to receive liraglutide treatment. The maximum duration of treatment of a single subject, from first trial product administration to last trial product administration will be 52 weeks, and the maximum dose will be 3.0 mg/day in part A and for children in part B with a body weight  $\geq 45$  kg. For children in part B with a body weight of  $< 45$  kg the maximum dose will be 2.4 mg/day.

At the first visit subjects and their LAR will be instructed in symptoms and treatment of hypoglycaemia, and in blood glucose measurements. The liraglutide dose will not be escalated if the subject experiences SMBG  $< 3.1$  mmol/L (56 mg/dL) or  $< 3.9$  mmol/L (70 mg/dL) in the presence of symptoms of hypoglycaemia, during the week prior to the dose escalation visit.

The following medications should not be used: orlistat, zonisamide, topiramate/phentermine, lorcaserin, phentermine and bupropion/naltrexone. Except for liraglutide as trial medication, GLP-1 receptor agonists cannot be prescribed during the trial. Metformin can only be used if the subject develops T2DM requiring an anti-diabetic agent as described in section [5.3.3](#).

Dosing in part B will be determined based on the results (including model-estimated steady state exposure) of the NN8022-4181 trial, a PK trial in children with obesity (Tanner stage below 2 (defined as Tanner stage 1 with or without premature adrenarche)), 7-11 years of age (both inclusive), and on the DMC review of PK data and safety data from the 16-week double-blind period from part A of this trial. If the dosing is different than for part A an amendment will be prepared.

Subjects in part A must have Tanner stage 2-5 pubertal development according to inclusion criterion 4. Pubertal development may have been hormonally induced with medical treatment.

Protocol: Liraglutide  
Trial ID: NN8022-4179  
UTN: U1111-1162-7884  
EudraCT no.: 2014-004415-37

~~CONFIDENTIAL~~

Date: 16 July 2020  
Version: 5.0  
Status: Final  
Page: 32 of 125

Novo Nordisk

### 5.3.1 Dose escalation

#### 5.3.1.1 Dose escalation part A

Dose escalation will be based on tolerability as assessed by the investigator.

Based on the results of the NN8022-3967 PK trial in pubertal adolescents with obesity (aged 12 to < 18 years) including model-estimated steady state exposure, treatment is planned to be initiated in part A with liraglutide/placebo 0.6 mg daily for one week and increased in weekly steps of 0.6 mg until a maximum tolerated dose (MTD) (as judged by the investigator) or a dose of 3.0 mg liraglutide/placebo is reached.

The trial product dose will be escalated only if the current dose is tolerated. If a subject has tolerability issues with the higher dose level (as judged by the investigator), it is allowed to lower to the previous dose level.

If a trial product dose is poorly tolerated, subjects are allowed to remain at a dose level for a maximum of 2 weeks. This extended time of one additional week is allowed at each dose level, i.e. the dose escalation process may take up to 8 weeks in total. It is at the discretion of the investigator to judge when the subject has reached MTD.

Escalation of the liraglutide/placebo dose is not allowed if the subject has a SMBG < 3.1 mmol/L (56 mg/dL) or < 3.9 mmol/L (70 mg/dL) in the presence of symptoms of hypoglycaemia during the week prior to the dose escalation visits. Hypoglycaemic episodes must be reported according to section [8.5.2](#).

Visits to the clinic occur weekly during the 4 weeks of dose escalation at V4-V7. Ideally, subjects will reach maximum dose of 3.0 mg at V7.

In those cases where more than one week is needed at any dose escalation step, the subject must still follow the visit schedule (V4-V7). For the remaining dose escalation step(s) after V7 it is at the discretion of the investigator to be in frequent contact (e.g. by phone/video conference) with the subject to ensure correct dose settings. The dose-escalation process must be completed no later than V8. Contacts regarding dose escalation must be documented in the subject's medical record and information about all dose levels must be recorded in the electronic case report form (eCRF).

#### 5.3.1.2 Dose escalation part B

Based on result of the safety and PK data of NN8022-4181 and part A of NN8022-4179, the recommendation for part B - PWS children (aged 6 to < 12 years) with obesity is to initiate treatment with liraglutide/placebo based on weight.

Protocol: Liraglutide  
Trial ID: NN8022-4179  
UTN: U1111-1162-7884  
EudraCT no.: 2014-004415-37

CONFIDENTIAL

Date: 16 July 2020  
Version: 5.0  
Status: Final  
Page: 33 of 125

Novo Nordisk

For children with a body weight  $\geq 45$  kg, dosing will be initiated with liraglutide/placebo 0.6 mg daily for one week and increased in weekly steps of 0.6 mg until a maximum tolerated dose (MTD) (as judged by the investigator) or a dose of 3.0 mg liraglutide/placebo is reached.

For children with a body weight  $< 45$  kg, dosing will be initiated with liraglutide/placebo 0.3 mg daily for one week and increased to 0.6 mg after the first week, thereafter the dose is increased in weekly steps of 0.6 mg until a MTD (as judged by the investigator) or a dose of 2.4 mg liraglutide/placebo is reached.

Escalation of the liraglutide/placebo dose is not allowed if the subject has a SMBG  $< 3.1$  mmol/L (56 mg/dL) or  $< 3.9$  mmol/L (70 mg/dL) in the presence of symptoms of hypoglycaemia during the week prior to the dose escalation visits.

Hypoglycaemic episodes must be reported according to Section [8.5.2](#).

Dose escalation will be based on tolerability as assessed by the investigator. The trial product dose will be escalated only if the current dose is tolerated. If a subject has tolerability issues with the higher dose level (as judged by the investigator), it is allowed to lower to the previous dose level.

If a trial product dose is poorly tolerated during the dose escalation period, subjects are allowed to remain at a dose level for an additional week, i.e. four times in total, thus the dose escalation will last for eight weeks in total as a maximum.

Visits and phone contacts to the clinic occur weekly during dose escalation.

Trial Product dose at V8 will be defined as MTD.

### 5.3.2 Maintenance

In the event that a subject experiences unacceptable intolerance as judged by the investigator, the liraglutide dose may be lowered to the next, lower dose level as needed:

- Part A and part B (children with a body weight  $\geq 45$  kg) (from 3.0 mg to 2.4 mg, from 2.4 mg to 1.8 mg, from 1.8 mg to 1.2 mg, and from 1.2 mg to 0.6 mg).
- Part B (children with a body weight  $< 45$  kg) (from 2.4 mg to 1.8 mg, from 1.8 mg to 1.2 mg, and from 1.2 mg to 0.6 mg and from 0.6 mg to 0.3 mg).

The reason for de-escalation of the liraglutide dose must be documented in the subject's medical record and transferred to the eCRF.

If the intolerance is due to intermittent illness or otherwise transient as judged by the investigator, the subject is allowed to return to the previous dose.

Protocol: Liraglutide  
Trial ID: NN8022-4179  
UTN: U1111-1162-7884  
EudraCT no.: 2014-004415-37

CONFIDENTIAL

Date: 16 July 2020  
Version: 5.0  
Status: Final  
Page: 34 of 125

Novo Nordisk

If a subject treated with the individual weight-based starting dose experiences unacceptable intolerance as judged by the investigator the subject must be discontinued from trial product (Section [8.1.8](#)).

### 5.3.3 Treatment of subjects who develop type 2 diabetes mellitus during the trial

If a subject develops T2DM during the course of the trial, he/she will be allowed to remain in the trial if glycaemic control can be achieved through diet and physical activity according to local standard of care. Furthermore, additional treatment with metformin is allowed at the discretion of the investigator.

If anti-diabetes treatment other than diet, physical activity and metformin is required for glycaemic control the trial product must be discontinued (sections [6.4](#) and [8.1.8](#))

### 5.4 Treatment after discontinuation of trial product

As liraglutide is not currently approved for treatment of obesity in the paediatric population, it will not be available to the subjects once the trial period ends. When subjects withdraw from or complete the trial, they should continue present or be switched to other suitable dietary and physical activity program at the discretion of the investigator.

### 5.5 Rationale for treatment

The rationale for the dose-escalating design is to mitigate gastrointestinal adverse events. A corresponding tolerability/PK/PD trial (NN2211-1800) in paediatric subjects with T2DM, age 10–17 years, with maximum dose of 1.8 mg liraglutide has been conducted as part of the Paediatric Investigation Plan (PIP) for Victoza® T2DM. In addition, a PK/PD trial NN8022-3967 in pubertal adolescents with obesity (aged 12 to < 18 years) has been completed as part of the PIP for liraglutide 3.0 mg for treatment of obesity. In trial (NN8022-4181), liraglutide, at doses up to 3.0 mg, was generally well tolerated in children with obesity without T2DM (aged 7-11 years); no unexpected safety or tolerability issues were detected. As in adults, liraglutide exposure increased with increasing drug dose.

The starting dose of 0.6 mg applied for part A of the current trial in adolescents with obesity and PWS is based on the tolerability results in trial NN2211-1800 and NN8022-3967. The maximum dose of 3.0 mg is the approved dose for the adult population with obesity, based on efficacy and safety evaluation from the phase 2 dose finding trial (NN8022-1807) and the phase 3a programme in adults.

The weight-based starting dose of 0.6 mg for children with body weight  $\geq$  45 kg and 0.3 mg for children with body weight < 45 kg applied for part B is based on the limited data in patients below 45 kg with liraglutide treatment. As a precautionary measure and to ensure comparable exposure at

Protocol: Liraglutide  
Trial ID: NN8022-4179  
UTN: U1111-1162-7884  
EudraCT no.: 2014-004415-37

~~CONFIDENTIAL~~

Date: 16 July 2020  
Version: 5.0  
Status: Final  
Page: 35 of 125

**Novo Nordisk**

the start of treatment the 0.3 mg starting dose with a cap of 2.4 mg/day as a maximum dose for subjects < 45 kg is introduced.

The treatment duration of 16 weeks is considered adequate for evaluation of the effect of liraglutide on the primary efficacy endpoint during the double-blind period. The 36-week open-label period will provide supportive information on the effect of liraglutide on other efficacy endpoints and establish the safety profile of liraglutide in this patient population. A placebo group is included in the trial to compare safety between placebo and liraglutide treatment. The s.c. injection is the route of administration intended for clinical use of liraglutide.

For more information, see the latest edition of the Investigator's Brochure for: Liraglutide (NN8022) in Weight Management or any updates hereof.

Protocol: Liraglutide  
Trial ID: NN8022-4179  
UTN: U1111-1162-7884  
EudraCT no.: 2014-004415-37

~~CONFIDENTIAL~~

Date:  
Version:  
Status:  
Page:

16 July 2020  
5.0  
Final  
36 of 125

**Novo Nordisk**

## 6 Trial population

### 6.1 Number of subjects

Number of subjects planned to be screened: 64 (part A: 38; part B: 26)

Number of subjects planned to be randomised: 57 (part A: 33; part B: 24)

Number of subjects expected to complete the trial: 45 (part A: 28; part B: 17)

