### **8.1.8 Discontinuation of trial product**

See section [6.4](#) for discontinuation of trial product criteria. For subjects with discontinuation of trial product, the investigator must at a minimum aim to:

- undertake procedures for the end of treatment visit (V19) as soon as possible and
- schedule a follow up visit (V20) two weeks later.

Depending on when the discontinuation of trial product takes place during the trial:

- If trial product is discontinued between V3 and V9, the subject should attend V10x (16 weeks after V3) and V19x (52 weeks ( $\pm$  5 days) after V3)
- If trial product is discontinued between V11 and V19, the subject should attend V19x (52 weeks ( $\pm$  5 days) after V3)

The end-of-trial form must be completed, and final drug accountability must be performed. A treatment discontinuation session must be made in the IV/WRS. The case book must be signed.

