### 17.1 Sample size calculation

This is a superiority trial comparing liraglutide to placebo. Based on previous experience the treatment effect after 52 weeks is expected to be considerable larger than after 16 weeks. Therefore the sample size calculation below focuses alone on the first co-primary endpoint.

It is difficult to assess the anticipated effect of liraglutide in BMI SDS in children and adolescents with PWS. It is anticipated that the effect is similar to the effect for adults.

The standard deviation (SD) is assessed based on publications and trial NN8022-3967 in adolescents with obesity aged 12–17 years. For the sample size scenarios, SDs of 0.15, 0.25 and 0.35 were investigated.

The effect of withdrawals is accounted for as a reduction of the anticipated treatment difference and increase of the SD. Since a conservative imputation method is planned for the main analysis of the primary endpoint, it is assumed that withdrawn subjects respond as if treated with placebo for the entire trial. The assumed withdrawal percentage at week 16 is 10% and 20% at week 52. This is lower than what was seen for trial NN8022-1839 in adults with obesity and adults with overweight. Since patients with Prader-Willi Syndrome are under close supervision by parents or institutional staff and for the lack of other therapeutic options, this assumption is considered reasonable. Let  $p_{WD}$  denote the probability of withdrawal. The adjustment for withdrawals is made by correcting the treatment difference  $\Delta$  and variance  $\sigma^2$  as

Protocol: Liraglutide  
 Trial ID: NN8022-4179  
 UTN: U1111-1162-7884  
 EudraCT no.: 2014-004415-37

~~CONFIDENTIAL~~

Date:  
 Version:  
 Status:  
 Page:

16 July 2020  
 5.0  
 Final  
 90 of 125

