**Table 17–1 Sample size calculations for different scenarios; total number of subjects**

Power	Treatment difference (completers)	SD		
		0.15	0.25	0.35
80%	-0.22	27	63	117
	-0.225	27	60	111
	-0.23	24	57	108
85%	-0.22	30	72	132
	-0.225	30	69	126
	-0.23	27	66	123
90%	-0.22	33	81	156
	-0.225	33	78	147
	-0.23	33	75	141

It seems realistic and conservative to assume a SD of 0.25 and a withdrawal rate of 10% after 16 weeks and 20% after 52 weeks. A withdrawal rate of 10% gives 57 subjects randomised. With this setting, a treatment difference of -0.23 corresponding to approximately a 5-6% decrease in BMI can be detected with a power of 80%. Assuming a withdrawal rate at 20% at week 52 a trial completion of 45 subjects, which is a regulatory requirement, is obtainable.

The distribution of the 57 subjects for randomisation on part A and B and the two treatment groups are shown in the table below.

Protocol: Liraglutide  
 Trial ID: NN8022-4179  
 UTN: U1111-1162-7884  
 EudraCT no.: 2014-004415-37

~~CONFIDENTIAL~~

Date: 16 July 2020  
 Version: 5.0  
 Status: Final  
 Page: 91 of 125

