**Novo Nordisk**

**Table 17–2 Overview of randomised subjects**

	Liraglutide	Placebo	Total Liraglutide and Placebo	Expected number of subjects to complete treatment (at least 80%)	Minimum PIP requirement of subjects to complete treatment
Part A	22	11	33	28	28
Part B	16	8	24	19	17
Total	38	19	57	47	45

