**Table 5-4 Statistical analysis to address primary objectives**

SI No.	Endpoints	Landmark visits	Endpoint type	Imputation approach and Statistical model	Analysis set	Sensitivity analyses
Primary Endpoint						
1	Change from baseline in BMI SDS	Week 16, Week 52	Continuous	J2R-MI ANCOVA	FAS	
 
• ANCOVA (LOCF)
 
• ANCOVA (BOCF)
 
• ANCOVA (no imputation, with 16-week (or 52 weeks) completers)
 
• MMRM
 

Due to the outbreak of the coronavirus (COVID-19), the primary endpoint assessments (body weight and height) for very few subjects could not be performed on-site at the end of the double-blind period of the trial – Visit 10 (Week 16) or at the end of the open-label period of the trial – Visit 19 (Week 52). It was recommended to have the body weight and height measured at the subject's family doctor, if possible, and alternatively to perform home weight and height measurements based on instructions provided. These measurements as well as measurements for subjects who were unable to perform or have body weight and height measured due to COVID-19 will not be part of the primary analysis but will be included in sub analysis. This is applicable only for part B as only subjects from part B were enrolled in the trial during the pandemic.

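### Does the mismatch in expected completers between protocol section 6.1 (28/17/45) and Table 17-2 (28/19/47) call for a change?

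*Protocol*

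**What the plan says.** Protocol section 6.1 plans 57 randomised subjects (33 in part A, 24 in part B) and then gives: "Number of subjects expected to complete the trial: 45 (part A: 28; part B: 17").

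Table 17-2 in section 17.1 has the same 57/33/24 and two completer columns. The first, headed "Expected number of subjects to complete treatment (at least 80"%), reads 28/19/47. The second, headed "Minimum PIP requirement of subjects to complete treatment", reads 28/17/45.

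Section 17.1 gives the only withdrawal rates: "The assumed withdrawal percentage at week 16 is 10% and 20% at week 52". It adds: "Assuming a withdrawal rate at 20% at week 52 a trial completion of 45 subjects, which is a regulatory requirement, is obtainable".

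Sections 1 and 6.6 give 28 and 17 as at-least numbers of evaluable subjects, and the trial continues until they are reached. Section 6.6 starts subject replacement if withdrawal exceeds the assumed 10% or 20%, and says that this is to meet the numbers required by the Paediatric Committee (PDCO).

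**The concern.** Two current sections of the same protocol give different expected completers, and the figures in 6.1 are exactly the minimum column of Table 17-2. A reader of 6.1 alone would infer 7 withdrawals among 24 in part B (29.2%), where section 17.1 assumes 20%. Part A looks odd too: 20% withdrawal from 33 leaves 26.4, not 28, and no lower rate is stated for part A. Version 5.0 was issued to align subject numbers across sections 1, 6.1, 6.6 and 17.1, so a leftover mismatch invites doubt about the rest.

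If the completer figures fed the sample size, a regulatory floor or an analysis, the trial could be under-recruited or misreported. The check is whether they do.

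**Working it through.** **1. Does N = 57 depend on expected completers?** Inputs from section 17.1: difference 0.23, SD 0.25, withdrawal p = 0.10, 2:1 allocation, two-sided 5%, 80% power.

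- Corrected difference: (1 − 0.10) × 0.23 = 0.207.
- Corrected variance: 0.25² + (2/3)(0.10)(0.90)(0.23²) = 0.0625 + 0.003174 = 0.065674, so SD = 0.2563.
- Smallest 2:1 total with 80% power: 57 (38 + 19), by the normal approximation and by the noncentral t. Power at 38/19 is 82.0% and 80.6% respectively. The noncentral-t version also matches all 27 cells of Table 17-1.

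The plan's figure reproduces, and no completer count enters it.

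**2. Completers at the stated 20%, against the printed figures.**

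| | Randomised | × 0.80 | Section 6.1 | Table 17-2 expected | Table 17-2 minimum |
|---|---|---|---|---|---|
| Part A | 33 | 26.4 | 28 (84.8%) | 28 (84.8%) | 28 |
| Part B | 24 | 19.2 | 17 (70.8%) | 19 (79.2%) | 17 |
| Total | 57 | 45.6 | 45 (78.9%) | 47 (82.5%) | 45 |

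The total of 45 in 6.1 and the part B figure of 19 in the table both follow from 20%. The part B figure of 17 in 6.1 does not; it is the minimum. Part A is 28 in both places, so the visible gap is two subjects in part B, carried into the total.

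**3. Is part A 28 an error?** The column header sets a floor of 80%, and 28/33 = 84.8% meets it. Part A was also well advanced by version 5.0 (July 2020). Its planned last visit was in May 2018 (section 7.1). The part B dosing in section 5.3.1.2 is introduced with "Based on result of the safety and PK data of NN8022-4181 and part A of NN8022-4179". The SAP says of its COVID-19 handling: "This is applicable only for part B as only subjects from part B were enrolled in the trial during the pandemic". So 28 may be an observed count, for which a prospective 20% is a poor yardstick. It may also be the larger of the 80% projection (26) and the minimum (28); the same rule gives 19 in part B and 47 in total. The documents do not say which.

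**4. Must trial completers be at least as many as treatment completers?** Section 6.1 counts completion of the trial, Table 17-2 completion of treatment. Section 8.1.8 keeps subjects who stop product in follow-up: "If trial product is discontinued between V11 and V19, the subject should attend V19x" at week 52. That suggests 45 cannot lie below 47. But placebo injections end at week 16 (protocol sections 5.1 and 11), and SAP Table 4-2 sets on-treatment for placebo at weeks 0 to 16. A placebo subject can complete treatment and then leave before week 52. As an illustration, assume the stated rates apply by arm:

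- Treatment completers: 38 × 0.80 + 19 × 0.90 = 30.4 + 17.1 = 47.5.
- Trial completers: 57 × 0.80 = 45.6.

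This order is possible, so the totals do not contradict each other on that ground. It is not a derivation of the table: part B would be 16 × 0.80 + 8 × 0.90 = 20.0, not 19.

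**5. Does anything else use the line?** The primary analysis takes the full analysis set with multiple imputation, and the completer sensitivity analysis takes whoever actually completed. Recruitment is governed by the at-least numbers. Nothing reads the expected-completer line in 6.1.

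**The case for a change.** The strongest case for a change is that version 5.0 existed to align these numbers and missed one line, that the repair costs a few words, and that section 6.6 holds two rules which can disagree. Taking evaluable to mean completed, and reading the replacement trigger per part:

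- Part A: 6 withdrawals of 33 is 18.2%, so there is no trigger, yet 27 completers miss the minimum of 28.
- Part B: 5 of 24 is 20.8%, so the trigger fires, yet 19 completers exceed the minimum of 17.

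Part A also has little slack. With independent 80% completion, the chance of at least 28 from 33 is 33%.

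The label mismatch stands as an editorial point, as do the unstated basis of part A 28 and the missing definition of evaluable. The argument from section 6.6 does not carry further. That section ties replacement to the PDCO numbers and then sets the per-part floors with a rule to continue until they are met. In the part A example that rule keeps recruitment open although the rate trigger is silent. The 33% therefore describes how often extra recruitment would be needed, not how often the floor would be missed. Nor does section 17.1 need a caveat: it claims only that a total of 45 is obtainable, and says nothing about part A.

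**Conclusion.** The discrepancy is real and small: two subjects, in part B (17 against 19) and so in the total (45 against 47). It is a clerical slip in section 6.1, where the PIP minima carry an expected label. The same 17 is called a minimum or at-least number in sections 1, 6.6 and 17.1, so a reader is unlikely to take 29% withdrawal as the plan. The sample size of 57, the 80% power, the minima of 28 and 17 and every analysis are untouched. Relabelling the line would alter nothing that the trial does or concludes, so no change is called for.

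This rests on two assumptions: that evaluable means completed, which the documents do not define, and that the continue-until rule in section 6.6 is applied per part, as it is written. The actual number of part A completers is not given, so whether 28 was observed or projected stays open. Neither answer affects the conclusion.
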